- **New malignancy**, including type and time to initial diagnosis, will be defined as any new malignancy, solid or hematologic, as reported to the transplant registry following the transplant date. Additional detail will be collected upon diagnosis, if available:

- TNM classification (for solid organ malignancies)
- Hematologic malignancy follow-up evaluation to be performed by the MAH as described in Section 12
- New or worsening (non-malignant) hematologic disorder, including time to diagnosis, may include the diagnosis of immune thrombocytopenia, autoimmune hemolytic anemia, autoimmune neutropenia, aplastic anaemia or other event, as reported to the transplant registry. Disorder status will be tracked at subsequent visits (e.g., stable, progressive, resolved), as applicable.
- **Mortality / Survival Status**, including time to event, will be based on the record in the respective registry:
 - Cause of death, as reported to the registries, will also be recorded
 - Date of last patient follow-up

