9.3.4 Effectiveness Outcome Variables

Variables described in this section are to: (i) characterize disease status at baseline and (ii) allow direct and indirect assessment of the effectiveness and durability of the transplant. Characterization of the type and number of transfusions (among TDT and SCD patients) and/or severe VOC events (SCD patients only) pre- and post-transplant allows determination of whether overt disease symptomatology has been corrected with the transplant. Hb measures, including total Hb concentration as well as Hb fractionation (e.g., % HbS among patients with SCD), allows tracking of graft uptake and function at a more cellular level than the symptomatic measures. Iron concentration and iron overload management are secondary measures of graft function, as cessation of primary symptomology (transfusion dependence) should lead to measurable decreases in iron burden and a reduced need for iron overload therapies over time. Measures of organ dysfunction at baseline and over time are also secondary measures of graft function as successful correction of the underlying genetic deficiency is expected to prevent further accumulation of organ damage over time and/or prevent new disease-related organ damage events from occurring. These measures encompass the core effectiveness assessment for the transplant.

The following effectiveness outcomes will be recorded:

- **Primary disease severity measures** will be recorded pre- and post-transplant as summarized in the schedule of data collection presented in Section 9.3.6. Specifically, pre-transplant these events will be quantified for the 1 year (12 months) preceding initiation of the conditioning regimen:
 - RBC transfusion events (TDT and SCD) to be defined as the receipt of RBCs for the purpose of primary disease management (i.e., anemia). Number of RBC transfusions and number of units transfused will be recorded pre- and post-transplant (as available) as summarized in the schedule of data collection. Time from HSCT to most recent transfusion will be recorded.
 - Severe VOC events (SCD only): Number of severe VOC events will be recorded pre- and post-transplant as summarized in the schedule of data collection presented in Section 9.3.6. Time from HSCT to most recent severe VOC event will be recorded.

Severe VOC events will include any/all of the following events:

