9.7.4 Effectiveness Analyses

Effectiveness analysis outcomes will be evaluated for each cohort from each registry for each post-transplant follow-up period. Analyses will be performed overall and in subgroups by patient age group, genotype, and/or other category, as appropriate and if sufficient data are available. Additional analyses may be performed for outcomes deserving further investigation if sufficient data are available. Statistical testing may be performed comparing the frequencies or rates of outcomes from the TDT Exa-cel and TDT Allo-HSCT Cohorts, and the SCD Exa-cel and SCD Allo-HSCT Cohorts, if sufficient data are available.

- For the primary disease severity measures, descriptive statistics for the number of events in the 1 year prior to the preparative regimen initiation and at each of the post-transplant follow-up periods will be reported:
 - Number of RBC transfusion events (TDT and SCD)
 - Number of severe VOC events (SCD only)

Proportions of patients who are RBC transfusion-free, severe VOC-free or severe VOC hospitalization-free (as appropriate) will also be reported at each timepoint of the post-transplant periods.

Time RBC transfusion-free or VOC-free, from Day 0 to the most recent event, will also be summarized.

- **Hb measures** (total Hb, % HbF, % HbS [where relevant]) will be summarized as continuous variables for each timepoint of the post-transplant period, with a 95% CI, among patients with an observation.
- **Iron concentration measures** (serum ferritin, LIC, CIC) will be summarized as continuous variables for each timepoint of the post-transplant period, with a 95% CI, among patients with an observation.

Absolute change from baseline may be calculated for patients with non-missing baseline and post-transplant years.

• New disease-related end-organ damage or dysfunction diagnoses will be summarized for each timepoint of the post-transplant period as the proportion of patients with a new diagnosis (i.e., categorical variables), with a 95% CI.

Cumulative diagnoses over the entire post-HSCT observation period may be reported for select diagnoses.

• Use of iron overload management tools (chelation therapy, phlebotomy) will be summarized for each timepoint of the post-transplant follow-up period as the proportion of patients receiving therapy (i.e., categorical variables).

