9.9 Limitations of the Research Methods

9.9.1 Limitations of Registry Data Collection

The transplant registries used for this study have definite strengths for the collection of real-world data, particularly for those outcomes that are transplant-specific such as neutrophil recovery and secondary malignancy development. While registry data to be collected for this study is very broad, it may not be as granular as clinical trial data. This is an expected limitation of observational, real-world studies. Where feasible, additional data collection is being integrated in consultation with the registry personnel, balancing appropriate level of detail in the data collection to meet the study objectives with the burden of time placed on transplant personnel and their ultimate willingness to participate in the study.

For example, it is deemed by the registries that collection of the laboratory results most proximal to the patient's data reporting period (e.g., 6 months, 1 year) is sufficient to identify any long-term abnormalities and allows to limit the burden of data entry placed on the transplant center personnel. While longitudinal laboratory results will only be collected at pre-specified timepoints, it is unlikely that safety events will be missed due to this limitation because a broad range of hard endpoints (i.e., disease diagnoses) are included in this study and uploaded into the registry by transplant center personnel.

In a similar manner, registries will collect comprehensive data on number of severe VOC events among patients with SCD in each reporting interval and time from HSCT to most recent severe VOC event but will not capture the date of each possible severe VOC event over the 15-year study duration. This approach was deemed to be optimal, allowing the capture of information necessary to meet the study objectives without limiting the feasibility of the study by the undue burden of data collection on the participating transplant centers.

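### Section 9.7.4 labels the interval from Day 0 to the most recent event as event-free time, so this one secondary summary is reversed or uninformative, depending on conventions the protocol does not state.

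*Protocol*

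**What the plan says.** The sentence at issue closes the disease severity bullet in Protocol Section 9.7.4: "Time RBC transfusion-free or VOC-free, from Day 0 to the most recent event, will also be summarized".

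Section 9.3.4 collects the matching quantities. For transfusion: "Time from HSCT to most recent transfusion will be recorded". For severe vaso-occlusive crises (VOC): "Time from HSCT to most recent severe VOC event will be recorded". Section 9.9.1 repeats the VOC variable, says that the number of severe VOCs per reporting interval is collected, and adds that the registries "will not capture the date of each possible severe VOC event over the 15-year study duration". The choice of the most recent event is therefore consistent across three sections. It cannot be read as a slip for the first event.

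Section 9.3.4 says the effectiveness variables are there to "allow direct and indirect assessment of the effectiveness and durability of the transplant". Section 9.3.3 also records "Date of last patient follow-up". No section says what value a patient without any event receives in the Section 9.7.4 summary.

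**The concern.** The collected variable is sound under its own name: time from transplant to the last event, where shorter is better. Section 9.7.4 presents it as time free of events, where a reader takes longer as better. A patient transfused monthly for 10 years would be summarized at about 10 years transfusion-free. A patient whose last transfusion was on Day 30 would be summarized at 30 days.

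This is the only summary in units of time for the disease severity measures in Section 9.7.4, and it is to be produced for both the exa-cel and the allo-HSCT cohorts. At stake is a table in the interim and final reports in which the cohort with more persistent events can appear the more durable.

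**Working it through.** The protocol gives no figure for this measure, so there is none to reproduce. The check concerns its direction.

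**Single patients, 15 years of follow-up (Section 9.7.1)**
- One event at 0.1 y, then none: measure = 0.1 y; last event to last follow-up = 14.9 y.
- Events about yearly until 14.9 y: measure = 14.9 y; last event to last follow-up = 0.1 y.
- No event: measure undefined; last follow-up from Day 0 = 15 y.

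**Constant event rate L over follow-up F, patients with at least one event (rates assumed)**

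Let g = 1/L − F·exp(−LF)/(1 − exp(−LF)). The expected time to the last event is F − g, and to the first event g.

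| Rate per year | Last event, F = 15 | First event, F = 15 | Last event, F = 5 |
|---|---|---|---|
| 0.05 | 8.43 | 6.57 | 2.60 |
| 0.2 | 10.79 | 4.21 | 2.91 |
| 1 | 14.00 | 1.00 | 4.03 |
| 12 | 14.92 | 0.08 | 4.92 |

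The protocol's measure rises with the event rate, while time to first event falls. If event-free patients are given full follow-up, the measure over 15 years is not monotone: 11.53 y at 0.05 per year, 10.58 at 0.1, 11.00 at 0.2 and 14.00 at 1.

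**Two cohorts, 90% and 70% cured**

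Assumed: 5 years of follow-up and failures transfused every 28 days, so their last transfusion falls on average 14 days before last contact, at 5 − 14/365.25 = 4.9617 y. The result turns on the cured patients.

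| Handling of cured patients | 90% cured | 70% cured | Reading |
|---|---|---|---|
| Last qualifying transfusion at Day 30 | 0.9×30/365.25 + 0.1×4.9617 = 0.57 y | 0.7×30/365.25 + 0.3×4.9617 = 1.55 y | reversed |
| No qualifying event, omitted | 4.96 y | 4.96 y | no information |
| No qualifying event, given full follow-up | 0.9×5 + 0.1×4.9617 = 4.996 y | 0.7×5 + 0.3×4.9617 = 4.989 y | right order, almost no contrast |

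In the first row the worse cohort looks 1.55/0.57 = 2.7 times better.

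**Same cohorts, most recent event (or Day 0 if none) to last follow-up**
- Cured patients last transfused at Day 30: 5 − 0.57 = 4.43 y and 5 − 1.55 = 3.45 y.
- Cured patients with no event: 0.9×5 + 0.1×0.0383 = 4.50 y and 0.7×5 + 0.3×0.0383 = 3.51 y.

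The order is right under either handling.

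**Simulated mixture over 15 years** (responders last transfused between days 20 and 60, failures transfused to the end; both assumed): the protocol's measure averages 0.84 y with 95% responders, 1.60 y with 90%, 4.56 y with 70%, 7.53 y with 50% and 14.96 y with none.

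**The case against.** The case for leaving the sentence alone has real content.

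- **Standing of the measure.** It is a supplementary description under a secondary objective, in a study that Section 8.2 calls hypothesis generating. No decision rule uses it, and the optional between-cohort testing in Section 9.7.4 concerns frequencies or rates. This stands.
- **Other outputs.** Section 9.7.4 also reports event counts per period and the proportions free of transfusion, severe VOC and VOC hospitalization. Table 2 collects these events annually through Year 15. A cohort with more failures would show it there. A reader might infer that the plan's durability result as a whole points the wrong way; the document does not support that.
- **Dependence on conventions.** A reader might also infer that the 2.7-fold reversal is what the plan will produce, or that patients with continuing events always score longest. The reversal needs cured patients to have a qualifying early transfusion. Section 9.3.4 says transfusion events are "to be defined as the receipt of RBCs for the purpose of primary disease management (i.e., anemia"), so peri-transplant support may or may not count. Scoring longest is guaranteed only among patients with an event.
- **Data limits.** It is tempting to say that time to first event is lost. The statement in Section 9.9.1 about uncaptured dates concerns severe VOC only, and counts per reporting interval locate the first event to within an interval for both event types. If the latest event time is recorded at each report, a first positive interval with a single event gives its time exactly.
- **The obvious replacement.** Time from the last event to last follow-up grows with follow-up. Enrollment runs over 3 to 5 years (Section 9.5), and loss to follow-up may be differential (Section 9.9.5). This stands and shapes the fix.

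None of this makes the label correct. Nor is it a detail left to the statistical analysis plan: the protocol states a definition, so a plan that follows it inherits the error and a plan that corrects it contradicts the protocol.

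**Conclusion.** The point holds in a limited form. The interval from Day 0 to the most recent event is not event-free time. Among patients with an event it runs opposite to its label, and it is undefined for patients without one.

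At cohort level, under the assumed 5 years and 28-day transfusion interval, 90% against 70% cured ranges from a reversal (0.57 against 1.55 y) through no contrast (4.96 against 4.96 y) to a negligible contrast in the right order (4.996 against 4.989 y). Which applies depends on the handling of event-free patients and peri-transplant transfusions, which the protocol does not settle.

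The defect is confined to one secondary descriptive line. It should be fixed, but it does not undermine the section's other effectiveness outputs or the study's primary safety objectives.

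**What to change.** Replace the sentence in Section 9.7.4 with one of the following, and carry it into the statistical analysis plan.

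1. **Relabel and complement.** Report the collected variable as time from transplant to most recent event, stating that shorter is better. With it, report event-free duration from the most recent event (or Day 0 if none) to last follow-up. Show this at common follow-up landmarks or alongside follow-up time, because it grows with follow-up.
2. **Time to first event.** Locate the first event from the counts per reporting interval and analyse it as interval-censored, with death as a competing event. State how early peri-transplant transfusions are handled.

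Under either option, state how patients with no event enter the summary.

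Both use data already planned: date of last follow-up (Section 9.3.3), time to most recent event and event counts (Section 9.3.4), and the visit schedule (Table 2). The cost is one sentence in the protocol, its counterpart in the analysis plan, and a little more analysis work, mostly for the interval-censored option.

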9.7.5 Other Analyses

Additional key outcomes will also be evaluated for each cohort from each registry for each time point of the post-transplant period. Findings will be summarized as categorical or continuous measures, as appropriate:

• Post-transplant complications

- Post-transplant health status measures
- Post-transplant disease-related therapies
- Post-transplant additional laboratory measures, including relevant CBC results at each available timepoint throughout the study duration
- Post-transplant pregnancies

In addition to all analyses of the pre-specified outcome variables (Section 9.3.3 through 9.3.5) for both the exa-cel and allogeneic HSCT cohorts, Serious Adverse Events (SAEs) among participating exa-cel recipients reported to the sponsor per Section 11 will be provided with each study report as a summary tabulation (proportion of exa-cel treated patients with SAE reports, by type) and in a listing format. Findings from the hematologic malignancy evaluation (Section 12) will also be provided, where available.

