8 RESEARCH QUESTIONS AND OBJECTIVES

8.1 Objectives

Primary

- 1. Evaluate long-term safety outcomes in patients who received exa-cel for treatment of TDT or SCD
- 2. Evaluate long-term safety outcomes in patients who received exa-cel for treatment of TDT or SCD in comparison to patients receiving allo-HSCT

Secondary

- 1. Evaluate long-term effectiveness outcomes in patients who received exa-cel for treatment of TDT or SCD
- 2. Evaluate long-term effectiveness outcomes in patients who received exa-cel for treatment of TDT or SCD in comparison to patients receiving allo-HSCT

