9.3.3 Safety Outcome Variables

Variables described in this section are specifically to characterize the safety of the transplant procedure; collection and reporting of these safety outcomes encompass the primary objective of the study.

Neutrophil recovery information will allow assessment of the initial function of the graft and identify instances of neutrophil engraftment failure. Platelet recovery information will allow characterization of any instances of delayed platelet recovery; the threshold used for defining platelet recovery in patients with SCD is higher compared to patients with β -thalassemia to protect individuals with SCD from thrombocytopenia-associated hematologic complications.⁷⁻¹¹ New malignancy diagnosis information will allow assessment of the risk of secondary malignancies post-transplant.¹² New or worsening hematologic disorder is an exploratory variable to assess any indication of bone marrow compartment regeneration abnormality.

The following safety outcomes will be recorded as summarized in the schedule of data collection presented in Section 9.3.6:

- Neutrophil recovery will be defined as the achievement of an absolute neutrophil count (ANC) of ≥500/mm³ (or ≥0.5 × 10⁹/L) for 3 consecutive measurements. Date of ANC recovery will be assigned as the date of the first of 3 consecutive measurements where the ANC is ≥500/mm³. Time to neutrophil recovery will be defined as number of days from the transplant date (Day 0) to the date of neutrophil recovery.
- Platelet recovery definition will differ based on the primary disease diagnosis:
 - For patients with β-thalassemia, platelet recovery will be defined as achievement of 3 consecutive measurements of platelets ≥20 × 10⁹/L after 7 days without platelet transfusion. Date of platelet recovery will be assigned as the first of the 3 consecutive measurements where platelets ≥20 × 10⁹/L. Time to platelet recovery will be defined as number of days from the transplant date (Day 0) to the date of recovery.
 - For patients with SCD, platelet recovery will be defined as achievement of 3 consecutive measurements of platelets \geq 50 × 10⁹/L after 7 days without transfusion. Date of platelet recovery will be assigned as the first of the 3 consecutive measurements where platelets \geq 50 × 10⁹/L. Time to platelet recovery will be defined as number of days from the transplant date (Day 0) to the date of recovery.

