 - Other [with write-in field] to allow flexibility over time, a write-in field will be available to capture additional therapies not specified at the time of study initiation
- Additional laboratory measures will be recorded pre- and post-transplant, as available, as summarized in the schedule of data collection presented in Section 9.3.6:
 - CBC
 - RBC count

- White blood cell count
- Hb (included in Section 9.3.4)
- Hematocrit
- Mean corpuscular volume
- Platelet count
- Reticulocyte count
- o Erythropoietin
- Soluble transferrin receptor
- Lactate dehydrogenase
- Liver function measures
 - Alanine transaminase / Alanine aminotransferase
 - Aspartate transferase / Aspartate aminotransferase
 - Bilirubin, Total
 - Bilirubin, Direct
 - Bilirubin, Indirect
- Glomerular filtration rate, estimated (eGFR)
- **Transplant-related complications,** including time to initial diagnosis, to be recorded post-transplant as summarized in the schedule of data collection presented in Section 9.3.6:
 - Infection (including site, organism)
 - Bleeding events (including site)
 - o Veno-occlusive disease / sinusoidal obstruction syndrome
 - o Non-infectious interstitial pneumonitis / idiopathic pneumonia syndrome
 - Graft-versus-host disease (acute, chronic)
- **Pregnancy report**, including delivery date, for patient or partner (outcomes: live birth, stillbirth, spontaneous abortion, elective or therapeutic abortion, not yet delivered, other).
 - For live births, if available, to also collect instances of small for gestational age, intrauterine growth retardation, other.

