9.3.6 Schedule of Data Collection

Data collection for each patient will occur on the following schedule: Baseline / Day 0 report, Day 100, 6-month and 1-year assessments, then annual assessments thereafter.

Data will be collected using registry standard and study-specific forms. Mapping of variables to standard collection or study-specific collection is included in Annex 4.

In addition to the data collection in the registry databases, all SAEs including hematologic malignancy, regardless of causality, among exa-cel recipients starting at the time of exa-cel

infusion and throughout the course of the study must be reported directly to the MAH (Sections 11 and 12).

		Post-HSCT Follow-up			
	Baseline /				Years 2 to 15
Registry Variable	Day 0	Day 100	Month 6	Year 1	(annual)
Informed consent / assent	Х				
Primary disease diagnosis					
β-thalassemia or SCD diagnosis	X				
Genotype	X				
Exposure					
Transplant date / Day 0 designation	Х				
Exa-cel or allo-HSCT	X				
Safety outcomes					
Neutrophil recovery		Х	Х		
Platelet recovery		Х	Х	X	
New malignancy		Х	Х	X	X
New or worsening hematologic disorder		Х	Х	X	Х
Mortality, cause		Х	X	Х	Х
Effectiveness outcomes					
Primary disease severity events (RBC transfusion, VOC) ^a	X	X	Х	X	Х
Hb measures (total Hb, HbF) a, b	Х	Х	X	X	X
Iron concentration measures ^{a, b}	Х	Х	X	X	X
Disease-related end organ damage / dysfunction diagnoses ^a	X	X	Х	X	Х
Iron overload management ^a	Х	Х	Х	X	X
Additional key variables					
Age at initial disease diagnosis	Х				
Age (at transplant)	Х				
Sex	Х				
Race, ethnicity (US only)	Х				
Country of transplant	Х				
Payor type (US only)	Х				
Performance score	Х	Х			
Comorbidity index	X				
Infused CD34 ⁺ Dose ^c	Х				
Donor type ^d	Х				
Cell source ^d	Х				
Mobilization and conditioning regimen	Х				
Height ^b	Х	Х	Х	Х	Х
Weight ^b	Х	Х	Х	Х	Х
Disease-related therapies ^a	X	X	Х	X	Х
Additional laboratory measures ^{a, b}	X	X	Х	X	Х
Transplant-related complications		X	Х	X	

Table 2Data Collection Schedule

Table 2Data Collection Schedule

		Post-HSCT Follow-up			
Degister Verichle	Baseline /	Dog 100	Month 6	Voor 1	Years 2 to 15
Registry variable	Day 0	Day 100	Month o	rear 1	(annuar)
Pregnancy, outcome		Х	X	Х	X

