9.7.1 Definition of Study Periods

For safety and effectiveness outcome analyses within the Exa-cel and Allo-HSCT Cohorts the pre-transplant and post-transplant periods will be defined as described below and illustrated in Figure 2:

- **Day 0 (transplant date)** is defined as the day of exa-cel product or allogeneic donor cell infusion, depending on cohort, as reported to the registries.
- **The pre-transplant / baseline period** will be broadly defined as the period prior to Day 0, with the length of the period varying depending on the study measures being evaluated:
 - For the *primary disease severity* measures (see Section 9.3.4 Effectiveness Outcome Variables) and *disease-related therapies* (see Section 9.3.5), the baseline period will be defined as 1 year prior to initiation of the conditioning regimen.
 - For *laboratory measures*, baseline will be defined as the non-missing measure most proximal, but prior to treatment initiation. This includes effectiveness measures such as total Hb, Hb fractionation (e.g., % HbS for SCD) and serum ferritin (see Section 9.3.4) as well other laboratory measures (see Section 9.3.5).
 - For pre-transplant *disease-related end-organ damage or dysfunction* (see Section 9.3.5) baseline will be defined as any time prior to the transplant.
 - Other variables such as patient demographics, pre-transplant height, weight and health status will be as reported at the most recent time point prior to transplant.
- The post-transplant period will continue for up to 15 years after the final enrolled patient's Day 0. For each patient, Year 1 will include events, new diagnoses or findings, and/or therapies initiated (or continued) within the first 365 days after Day 0; Year 2 will include the same occurring from patient day 366 to day 730, etc. Year 1 will further include the following time intervals based on existing transplant registry reporting: Day 0 to Day 100, Day 100 to 6 months, and 6-month to 1-year reporting. All patients, both exa-cel treated or comparator, will be followed for up to 15 years. Patients will be censored to last reported timepoint only after 2 years of loss to follow-up.

Figure 2 Study Periods

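### Table 2 stops scheduling transplant-related complications at Year 1, although Section 9.7.5 plans to evaluate them throughout follow-up; late non-fatal complications after allo-HSCT have no stated collection route

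*Protocol*

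**What the plan says.** Section 9.3.5 of the protocol defines transplant-related complications as infection, bleeding events, veno-occlusive disease, non-infectious pneumonitis and "Graft-versus-host disease (acute, chronic"). It does not limit the list to one cohort. It sets the timing by reference: "including time to initial diagnosis, to be recorded post-transplant as summarized in the schedule of data collection presented in Section 9.3.6".

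Section 9.3.6 gives the reporting schedule as "Baseline / Day 0 report, Day 100, 6-month and 1-year assessments, then annual assessments thereafter". In Table 2 the row "Transplant-related complications" is marked at Day 100, Month 6 and Year 1, and the column for Years 2 to 15 is empty.

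Section 9.7.5 then states: "Additional key outcomes will also be evaluated for each cohort from each registry for each time point of the post-transplant period". Post-transplant complications are the first item listed. Section 9.7.1 fixes the length of the period: "All patients, both exa-cel treated or comparator, will be followed for up to 15 years".

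The second primary objective in Section 8.1 is to "Evaluate long-term safety outcomes in patients who received exa-cel for treatment of TDT or SCD in comparison to patients receiving allo-HSCT". Section 9.3.3 ties that objective to its own list of outcomes: "collection and reporting of these safety outcomes encompass the primary objective of the study". Complications are not on that list.

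**The concern.** The analysis section and the collection schedule do not match. Read literally, Section 9.7.5 needs complications data in every follow-up year, and Table 2 supplies them for the first year only.

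The mismatch does not fall equally on the two treatments. Exa-cel is given as an autologous transplant, so GVHD is in substance a harm of the comparator (an inference; the protocol does not label it as confined to the Allo-HSCT Cohorts). The other route for late serious events, SAE reporting to the MAH, covers exa-cel recipients only. A non-fatal serious infection in Year 4 would therefore appear in the study reports for an exa-cel patient, while the same event in an allo-HSCT patient need not appear anywhere. In a study meant to describe long-term outcomes beside allo-HSCT, that makes the comparator's late course look cleaner than it was.

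**Working it through.** **Is the blank cell real?** Tables can be damaged when a PDF is read by program, so the neighbouring rows were checked. Laboratory measures, disease-related therapies and pregnancy, which sit next to this row, keep their mark for Years 2 to 15. So do new malignancy, hematologic disorder and mortality. Neutrophil recovery is marked at Day 100 and Month 6 only, and platelet recovery to Year 1, so the table uses blank cells deliberately. Loss of a mark in extraction is unlikely.

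**Count of reports** (schedule from Section 9.3.6).
- First-year reports: Day 100, Month 6, Year 1 = 3
- Annual reports, Years 2 to 15: 15 − 1 = 14
- Total post-transplant reports: 3 + 14 = 17
- Complications scheduled: 3 / 17 = 17.6%
- Complications not scheduled: 14 / 17 = 82.4%
- Follow-up years without scheduled collection: 14 / 15 = 93.3%

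**What can still be seen after Year 1.** Each route stated in the protocol, by cohort:

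| Event after Year 1 | Exa-cel | Allo-HSCT |
|---|---|---|
| Fatal complication | Cause of death, to Year 15 (9.3.3, Table 2) | Cause of death, to Year 15 (same) |
| Serious, non-fatal | SAE report to the MAH, tabulated in each report (9.1, 9.7.5, 11.3) | No stated route |
| Non-serious | No stated route | No stated route |
| Persistence or resolution of chronic GVHD | Not expected (autologous) | No stated route |

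The second and fourth rows carry the asymmetry. In both, the unseen events belong to the comparator, so the direction is towards a more favourable picture of allo-HSCT.

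**What is not affected.** New malignancy, hematologic disorder and mortality are scheduled through Year 15 in all cohorts. Neutrophil and platelet recovery are early outcomes, collected early. The pooled analyses at 5, 10 and 15 years concern the Section 9.3.3 outcomes, so they lose nothing.

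**Size of the effect.** The documents give neither the incidence of chronic GVHD nor the share that begins or persists after Year 1. The number of missed events cannot be derived from them.

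**The case against.** The strongest reply is that the protocol already says which passage governs. Section 9.3.5 sends the timing of complications to Table 2, and the sentence in Section 9.7.5 is a generic opening. Section 9.7.3 uses similar wording for all safety outcomes although neutrophil recovery is scheduled only to Month 6. Performance score, a health-status measure, stops at Day 100. On this reading the phrase means each time point at which the variable is collected, and the conflict is loose wording. That much stands: the sections can be read together. But such a reading leaves a 15-year comparative study with no late complications data for the comparator, and Section 9.9 does not disclose this among the limitations.

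A reader might infer that the primary safety comparison itself is compromised. The documents do not support that. Section 9.3.3 attaches the primary objective to its own outcomes, and Section 9.3.5 treats complications as supporting variables.

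A reader might also infer that late complications are never recorded. That is too strong: fatal cases show up through cause of death in all cohorts, and serious ones in exa-cel recipients through SAE reports.

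The standard registry forms may ask about GVHD after Year 1. The Annex 4 forms and mapping are stand-alone documents not at hand, so this cannot be excluded. If they do ask, Table 2 is incomplete and correcting it costs almost nothing.

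Finally, Section 9.9.1 gives limiting the burden on centres as a design principle. It is a fair consideration, but the protocol does not invoke it for this row.

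**Conclusion.** The point holds in a limited form. Table 2 and Section 9.7.5 need to be reconciled: complications are scheduled at 3 of 17 post-transplant reports and are absent from 14 of 15 years. The substantive gap is non-fatal chronic GVHD and serious infection after Year 1 in allo-HSCT patients, for which the protocol states no collection route. The long-term description of complications against allo-HSCT is asymmetric in the comparator's favour.

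This rests on two assumptions: that some such events begin or persist after Year 1, and that no unseen form collects them. A percentage understatement of chronic GVHD is tempting to quote, but it would only restate whatever late share one assumed. The amount must be left unquantified.

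This should be fixed as a cheap improvement to a supporting analysis. It is not a defect in a key safety outcome.

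**What to change.** Extend the complications row of Table 2 to Years 2 to 15 in all four cohorts, at minimum for chronic GVHD status (new, ongoing, resolved) and serious infection. Summarise chronic GVHD by cumulative incidence with death as a competing event, the method Section 9.7 already adopts for selected safety outcomes. Collection would then run at 17 of 17 reports for those items.

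The cost is a small added data-entry burden. The annual report is already completed to Year 15, and Section 9.3 says the study-specific forms will be finalised only upon protocol approval. Data not collected prospectively may be hard to recover years later.

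If the sponsor means to stop at Year 1, Section 9.7.5 should say that complications are evaluated through Year 1 only, and Section 9.9 should state that late complications are not compared between exa-cel and allo-HSCT.
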